10.4. Appendix 4: Contraceptive and Barrier Guidance

10.4.1. Male Participant Reproductive Inclusion Criteria

Male participants are eligible to participate if they agree to the following requirements during the intervention period and for at least 28 days after the last dose of study intervention, which corresponds to the time needed to eliminate reproductive safety risk of the study intervention(s):

• Refrain from donating sperm.

PLUS either:

• Be abstinent from heterosexual intercourse as their preferred and usual lifestyle (abstinent on a long-term and persistent basis) and agree to remain abstinent.

OR

- Must agree to use contraception/barrier as detailed below:
 - Agree to use a male condom, and should also be advised of the benefit for a
 female partner to use a highly effective method of contraception, as a condom
 may break or leak, when having sexual intercourse with a WOCBP who is not
 currently pregnant.
- In addition to male condom use, a highly effective method of contraception may be considered in WOCBP partners of male participants (refer to the list of highly effective methods below in Section 10.4.4).

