Days Relative to Day 1	Day -28 to Day -3	Day -2	Day -1	Day 1		ay 2	Day 3	Day 4	Visit: Day 8±1	Contact: 28-35 days		All screening should be done ≤28 days before the first dose. Day relative to start of study intervention (Day 1). Day 1 activities at time=0 hour are prior to the dose, except				
Hours After Dose				0	24	24 36		72		v		for study intervention administration. On-site follow-up visit occurs on Day 8±1 after administration of the final dose of study intervention. Follow-up may occur via telephone contact and must occur 28 to 35 days after administration of the final dose of study intervention.				
Contraception check	X	X	X					X	X	X	X	Contraception only required for male study participants. Contraceptive guidance is outlined in Appendix 4. If performed on Day -2 at admission, assessment is not needed on Day -1				
COVID-19 related measures		X	X	X	X		X	X	X		X	Per CRU procedures.				
CRU discharge					XX			X				Participants may be asked to remain at the CRU after completion of Day 4 activities at the discretion of the investigator or if safety, tolerability, or PK data dictate the need to prolong inpatient stay at the CRU				
Serious and nonserious AE monitoring	X	\rightarrow	\rightarrow	\rightarrow	\rightarrow	\rightarrow	\rightarrow	\rightarrow	\rightarrow	X	X	See Section 8.4.3 for follow-up AE and SAE assessments.				
Physical exam	X	X		able 2				X	X		X	Complete PE at Screening or upon admission for a participant's first period in the study; at all other time points, brief PE performed for findings during previous exam or new/open AEs, at investigator discretion. Including height and weight only at screening See Section 8.3.1 for additional information.				
Neurological examination				See Table	X				X		X	Complete neurological exam for timepoints on Day 1 (see Table 2) and 24 hours after dosing on Day 1. At other time points, neurological exam at investigator discretion. See Section 8.3.2 for additional information.				
Respiratory rate					X		X	X	X		X	Single assessment at all timepoints See Section 8.3.3 for additional details.				

 Table 1.
 Study Schedule of Assessment

Visit Identifier Abbreviations used in this table may be found in Appendix 10.	Screen]	Period 1 In-	l to F -patio		14		Foll	ow-Up	ET	Notes				
Days Relative to Day 1	Day -28 to Day -3	Day -2	Day -1	Day 1		ay 2	Day 3	Day 4	Visit: Day	Contact: 28-35		All screening should be done ≤28 days before the first dose. Day relative to start of study intervention (Day 1).				

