4.2. Scientific Rationale for Study Design

The population planned for this study will be healthy males and females of non-childbearing potential. Female participants will be confirmed not to be of childbearing potential because embryo-fetal development toxicity studies with PF-07328948 have not been conducted. In male participants, appropriate measures are expected to be followed to minimize potential transfer of PF-07328948 via semen to partners (see Appendix 4).

Because this is the first time PF-07328948 will be administered to humans, an escalating single, oral dose, crossover design is planned with careful assessment and ongoing review of safety, tolerability, and PK data of PF-07328948. Precautionary sentinel dosing will also be utilized in any period evaluating escalating doses of PF-07328948 to ensure that safety and tolerability data in a subset of 2 participants within each period supports testing additional participants in that period. In each period, approximately 6 participants are planned to receive PF-07328948, and approximately 2 participants are planned to receive placebo, with all the participants at the end of the study having received up to 4 doses of PF-07328948 and up to 2 placebo. The crossover design permits both within- and between-participants assessments of safety, tolerability, and PK at multiple dose levels and placebo.

In addition, the highest anticipated C_{max} and AUC_{24} of PF-07328948 will not exceed the pre-defined human exposure stopping limits nor exceed the highest feasible total daily dose Eurthermore, to permit an unbiased assessment of safety, the administration of both PF-07328948 and placebo in each period will be double-blinded to both site staff (except those involved in preparation of doses) as well as participants. To permit real-time review of the safety, tolerability, and PK data, a limited number of sponsor study team members will be unblinded.

CCI

. As a BDK inhibitor/degrader,

PF-07328948 is expected to inhibit BDK-mediated phosphorylation of BCKDH enzyme complex, resulting in an increase in BCAA/BCKA catabolism and a decrease in circulating BCAA and BCKA levels. As protein intake is known to impact plasma BCAA/BCKA levels, CCI

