4.2.1. Choice of Contraception/Barrier Requirements

Human reproductive safety data are not available for PF-07328948. Therefore, the use of a highly effective method of contraception is required for male study participants and is recommended for partners of male study participants who are WOCBP (see Appendix 4).

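### The condom sentence in Protocol Section 10.4.1 can be read as leaving out pregnant partners, and it should be split so that they are clearly covered

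*Protocol*

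**What the plan says.** **Purpose (Protocol Section 4.2).** Women in the study must be of non-childbearing potential because "embryo-fetal development toxicity studies with PF-07328948 have not been conducted". For men, "appropriate measures are expected to be followed to minimize potential transfer of PF-07328948 via semen to partners", with a pointer to Appendix 4. That statement speaks of partners in general and sets no limit by pregnancy status.

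**Rule (Section 10.4.1).** Men accept the conditions "during the intervention period and for at least 28 days after the last dose of study intervention". A man who is not abstinent agrees to contraception or a barrier. One sentence then does three things: it requires a male condom, it has the man told that a female partner may benefit from a highly effective method because condoms can fail, and it closes with "when having sexual intercourse with a WOCBP who is not currently pregnant". The next bullet reads "In addition to male condom use, a highly effective method of contraception may be considered in WOCBP partners of male participants".

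**Related text.**
- Section 4.2.1 says that a highly effective method "is required for male study participants and is recommended for partners of male study participants who are WOCBP".
- The note to the contraception check in Table 1 (Section 1.3) says "Contraception only required for male study participants" and refers to Appendix 4 for guidance.
- Section 5.3.1 has the investigator confirm a method from the list in Section 10.4.4, and has the participant call if a partner's pregnancy is known or suspected.
- Inclusion criterion 1 (Section 5.1) refers to Section 10.4.1 for men.

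**The concern.** A condom serves two separate aims here: preventing conception and keeping drug in semen away from a partner. A limit to partners who are not pregnant suits the first aim. It does not suit the second, because a pregnant partner already carries the fetus for which no developmental toxicity data exist.

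If site staff take the closing clause as the condition on the condom, a non-abstinent man whose partner is pregnant is not told to use one, and they will have followed the protocol as written. Staff who take it the other way will tell him to use one. A protective measure in a first-in-human study should not depend on how one clause is parsed. Reporting under Section 8.4.5.1 comes after exposure and does not prevent it.

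**Working it through.** The plan gives no figure on this point and no arithmetic applies. The check sets the passages side by side.

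1. **Is a pregnant partner within the term WOCBP?** Section 10.4.3 treats a woman as fertile from menarche to menopause unless permanently sterile. Pregnancy is not among its non-WOCBP categories. A pregnant partner is therefore normally a WOCBP, and the words about not being pregnant in Section 10.4.1 remove a group that the term would otherwise include.

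2. **Reading A: the clause governs the condom.** In its favour, the person having intercourse is most easily taken to be the male participant, and the clause is the only wording in the sentence that says when the condom is to be used. Result: a condom is required only with a non-pregnant WOCBP, so pregnant partners are left out and the purpose in Section 4.2 is not met for them.

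3. **Reading B: the clause governs only the advice.** In its favour, once the aside about condom failure is set apart, the clause directly follows the advice on the partner's method, and that advice makes sense only for a WOCBP who is not pregnant. Result: the condom duty has no partner limit, pregnant partners are covered, and there is no gap.

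4. **Does other text settle it?**
   - The parent bullet in Section 10.4.1, which introduces the barrier requirement, has no partner limit. This favours B.
   - The next bullet, "In addition to male condom use, a highly effective method of contraception may be considered in WOCBP partners of male participants", takes condom use as given and ties WOCBP only to the extra method. This favours B, but it sets no condom duty of its own.
   - Section 4.2.1 puts the requirement on the man without a partner limit and ties WOCBP to the recommendation for partners. This favours B as an aid to reading, but it concerns a highly effective method and does not mention condoms.
   - Section 4.2 speaks of partners generally. This favours B as a statement of purpose, but it leaves the measures to Appendix 4.
   - Section 5.3.1 can bring a partner's pregnancy to light, but does not say which condom rule then applies. The list in Section 10.4.4 contains no condom. Its two headings for highly effective methods are for WOCBP partners, so the omission says nothing about intent.

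5. **Result.** The surrounding text leans towards B, while the sentence that creates the duty remains open to A. No available passage says in terms that a condom is, or is not, required with a pregnant partner.

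**The case against.** The strongest reply is that a fair reader would reach Reading B. Section 4.2 states the aim and sends the reader to Appendix 4, and the parent bullet, the following bullet and Section 4.2.1 all point the same way. This largely stands. It means that a deliberate exemption for pregnant partners, which a reader might infer from the closing clause, is not supported by the documents. It does not remove the ambiguity in the operative sentence.

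A reader might also infer from Section 5.3.1 that condom use is never checked. The documents do not support that either. Table 1 points the contraception checks to the whole of Appendix 4, and inclusion criterion 1 makes agreement to Section 10.4.1 a condition of entry. What remains is narrower: Section 5.3.1 itself names only the Section 10.4.4 list.

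It can further be said that no harm has been shown and that other documents may state the rule. Both are fair. The number of men with a pregnant partner is unknown and could be zero. The closing part of Section 4.2, the investigator's brochure and the consent form were not available for this review. Even so, the protocol itself judged semen transfer worth limiting, and an eligibility requirement should be clear where it is stated.

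**Conclusion.** The point holds as an ambiguity: under one reading of Section 10.4.1 pregnant partners fall outside the condom requirement and the purpose in Section 4.2 is not met for them; under the other there is no gap. The documents do not establish which reading sites apply.

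The size of any harm cannot be estimated. The documents give no concentration of drug in semen, no developmental toxicity results and no count of affected men. The number of contraception checks or of participants still to be dosed would not stand in for it. No endpoint, analysis or dose decision is affected.

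This is a cheap improvement of low severity. The conclusion assumes that the text not available for this review does not already state the rule for pregnant partners. If it does, the edit only brings Section 10.4.1 into line with it.

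**What to change.** In Section 10.4.1, split the sentence in two:

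- **Condom:** non-abstinent male participants use a condom during intercourse with any partner who is pregnant or is a WOCBP, for the restriction period already set ("during the intervention period and for at least 28 days after the last dose of study intervention").
- **Advice:** the benefit of an added highly effective method is explained for partners who are WOCBP and not pregnant. The non-pregnancy limit appears only here.

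This wording does not extend the duty to postmenopausal or permanently sterile partners, for whom the embryo-fetal concern does not arise.

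As a minor alignment, have Section 5.3.1 refer to Section 10.4.1 for the condom as well as to the list in Section 10.4.4. Table 1 already points the checks to all of Appendix 4.

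The cost is one split sentence, one cross-reference, and matching consent wording if needed. The downside is a small added restriction for non-abstinent men with a pregnant partner. No visits, samples or participants are added.

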10.4.2. Female Participant Reproductive Inclusion Criteria

The criteria below are part of inclusion criterion 1 (Age and Sex; Section 5.1) and specify the reproductive requirements for including female participants. Refer to Section 10.4.4 for a complete list of contraceptive methods permitted in the study.

A female participant is eligible to participate if she is not pregnant or breastfeeding and is not a WOCBP (see definition in Section 10.4.3).

The investigator is responsible for review of medical history, menstrual history, and recent sexual activity to decrease the risk for inclusion of a woman with an early undetected pregnancy.

10.4.3. Woman of Childbearing Potential

A woman is considered fertile following menarche and until becoming postmenopausal unless permanently sterile (see below).

If fertility is unclear (eg, amenorrhea in adolescents or athletes) and a menstrual cycle cannot be confirmed before the first dose of study intervention, additional evaluation should be considered.

Women in the following categories are not considered WOCBP:

- 1. Premenopausal female with 1 of the following:
 - Documented hysterectomy;
 - Documented bilateral salpingectomy;
 - Documented bilateral oophorectomy.

For individuals with permanent infertility due to a medical cause other than the above (eg, mullerian agenesis, androgen insensitivity), investigator discretion should be applied to determining study entry.

Note: Documentation for any of the above categories can come from the site personnel's review of the participant's medical records, medical examination, or medical history interview. The method of documentation should be recorded in the participant's medical record for the study.

- 2. Postmenopausal female.
 - A postmenopausal state is defined as no menses for 12 months without an alternative medical cause. In addition:
 - A high FSH level in the postmenopausal range must be used to confirm a postmenopausal state in women under 60 years old and not using hormonal contraception or HRT.
 - A female on HRT and whose menopausal status is in doubt must discontinue HRT to allow confirmation of postmenopausal status before study enrollment.

10.4.4. Contraception Methods

Contraceptive use by men or women should be consistent with local availability/regulations regarding the use of contraceptive methods for those participating in clinical trials.

The following contractive methods are appropriate for this study:

Highly Effective Methods That Have Low User Dependency (for WOCBP partners of male participants)

1. Implantable progestogen-only hormone contraception associated with inhibition of ovulation.

- 2. Intrauterine device.
- 3. Intrauterine hormone-releasing system.
- 4. Bilateral tubal occlusion.
- 5. Vasectomized partner:
 - Vasectomized partner is a highly effective contraceptive method provided that the partner is the sole sexual partner of the WOCBP and the absence of sperm has been confirmed. If not, an additional highly effective method of contraception should be used. The spermatogenesis cycle is approximately 90 days.

Highly Effective Methods That Are User Dependent (for WOCBP partners of male participants)

- 6. Combined (estrogen- and progestogen-containing) hormonal contraception associated with inhibition of ovulation:
 - Oral;
 - Intravaginal;
 - Transdermal.
- 7. Progestogen-only hormone contraception associated with inhibition of ovulation:
 - Oral;
 - Injectable.

Sexual Abstinence

8. Sexual abstinence is considered a highly effective method only if defined as refraining from heterosexual intercourse during the entire period of risk associated with the study intervention. The reliability of sexual abstinence needs to be evaluated in relation to the duration of the study and the preferred and usual lifestyle of the participant.

10.5. Appendix 5: Genetics

Use/Analysis of DNA

- Genetic variation may impact a participant's response to study intervention, susceptibility to, and severity and progression of disease. Therefore, where local regulations and IRBs/ECs allow, a blood sample will be collected for DNA analysis.
- The scope of the genetic research may be narrow (eg, 1 or more candidate genes) or broad (eg, the entire genome), as appropriate to the scientific question under investigation.
- The samples may be analyzed as part of a multistudy assessment of genetic factors involved in the response to study intervention or study interventions of this class to understand treatments for the disease(s) under study or the disease(s) themselves.
- The results of genetic analyses may be reported in the CSR or in a separate study summary, or may be used for internal decision making without being included in a study report.
- The sponsor will store the DNA samples in a secure storage space with adequate measures to protect confidentiality.
- The samples will be retained as indicated:
- Retained samples will be stored indefinitely or for another period as per local requirements.
- Participants may withdraw their consent for the storage and/or use of their Retained Research Samples at any time by making a request to the investigator; in this case, any remaining material will be destroyed. Data already generated from the samples will be retained to protect the integrity of existing analyses.
- Samples for genetic research will be labeled with a code. The key between the code and the participant's personally identifying information (eg, name, address) will be held securely at the study site.

10.6. Appendix 6: Liver Safety: Suggested Actions and Follow-Up Assessments Potential Cases of Drug-Induced Liver Injury

Humans exposed to a drug who show no sign of liver injury (as determined by elevations in transaminases) are termed "tolerators," while those who show transient liver injury but adapt are termed "adaptors." In some participants, transaminase elevations are a harbinger of a more serious potential outcome. These participants fail to adapt and therefore are "susceptible" to progressive and serious liver injury, commonly referred to as DILI. Participants who experience a transaminase elevation above 3 × ULN should be monitored more frequently to determine if they are "adaptors" or are "susceptible."

In the majority of DILI cases, elevations in AST and/or ALT precede T bili elevations (>2 × ULN) by several days or weeks. The increase in T bili typically occurs while AST/ALT is/are still elevated above 3 × ULN (ie, AST/ALT and T bili values will be elevated within the same laboratory sample). In rare instances, by the time T bili elevations are detected, AST/ALT values might have decreased. This occurrence is still regarded as a potential DILI. Therefore, abnormal elevations in either AST OR ALT in addition to T bili that meet the criteria outlined below are considered potential DILI (assessed per Hy's law criteria) cases and should always be considered important medical events, even before all other possible causes of liver injury have been excluded.

The threshold of laboratory abnormalities for a potential DILI case depends on the participant's individual baseline values and underlying conditions. Participants who present with the following laboratory abnormalities should be evaluated further as potential DILI (Hy's law) cases to definitively determine the etiology of the abnormal laboratory values:

- Participants with AST/ALT and T bili baseline values within the normal range who subsequently present with AST OR ALT values ≥3 × ULN AND a T bili value ≥2 × ULN with no evidence of hemolysis and an alkaline phosphatase value <2 × ULN or not available.
- For participants with baseline AST **OR** ALT **OR** T bili values above the ULN, the following threshold values are used in the definition mentioned above, as needed, depending on which values are above the ULN at baseline:
 - Preexisting AST or ALT baseline values above the normal range: AST or ALT values ≥2 times the baseline values AND ≥3 × ULN; or ≥8 × ULN (whichever is smaller).
 - Preexisting values of T bili above the normal range: T bili level increased from baseline value by an amount of $\ge 1 \times ULN$ or if the value reaches $\ge 3 \times ULN$ (whichever is smaller).

Rises in AST/ALT and T bili separated by more than a few weeks should be assessed individually based on clinical judgment; any case where uncertainty remains as to whether it represents a potential Hy's law case should be reviewed with the sponsor.

The participant should return to the investigator site and be evaluated as soon as possible, preferably within 48 hours from awareness of the abnormal results. This evaluation should include laboratory tests, detailed history, and physical assessment.

In addition to repeating measurements of AST and ALT and T bili for suspected Hy's law cases, additional laboratory tests should include albumin, CK, direct and indirect bilirubin, GGT, PT/INR, total bile acids, and alkaline phosphatase. Consideration should also be given to drawing a separate tube of clotted blood and an anticoagulated tube of blood for further testing, as needed, for further contemporaneous analyses at the time of the recognized initial abnormalities to determine etiology. A detailed history, including relevant information, such as review of ethanol, acetaminophen/paracetamol (either by itself or as a coformulated product in prescription or over-the-counter medications), recreational drug, or supplement (herbal) use and consumption, family history, sexual history, travel history, history of contact with a jaundiced person, surgery, blood transfusion, history of liver or allergic disease, and potential occupational exposure to chemicals, should be collected. Further testing for acute hepatitis A, B, C, D, and E infection, liver imaging (eg, biliary tract), and collection of serum samples for acetaminophen/paracetamol drug and/or protein adduct levels may be warranted.

All cases demonstrated on repeat testing as meeting the laboratory criteria of AST/ALT and T bili elevation defined above should be considered potential DILI (Hy's law) cases if no other reason for the LFT abnormalities has yet been found. Such potential DILI (Hy's law) cases are to be reported as SAEs, irrespective of availability of all the results of the investigations performed to determine etiology of the LFT abnormalities.

A potential DILI (Hy's law) case becomes a confirmed case only after all results of reasonable investigations have been received and have excluded an alternative etiology.

